3.4 STUDY CALENDAR

Cycle is 28 days. A time window of up to 7 days before or after the scheduled visit day will be permitted in order to accommodate weekends, holidays, travel delays, inclement weather and other such unexpected events.

Screening for eligibility	
Within 4 weeks prior to enrollment	
 • 24-hour urine collection for urine protein, urine creatinine and urine albumin • HIV antibody • Radiological evaluations¹ • Histopathological confirmation of neuroendocrine tumors
Within 2 weeks prior to enrollment	
 • Hemoglobin A1C • 12- lead ECG • CBC, Chemistries², INR, Lipid panel (fasting) • Clinical Assessments³
Within 3 days prior to enrollment	
 • Serum or urine HCG (in women of childbearing potential only)
Enrollment	

 • Patient signs consent • Advance Directive⁴ 	
Baseline	
Tests need not be repeated if they have been done during the appropriate timeframe at screening	
Within 4 weeks prior to treatment initiation	
 • Hepatitis B and C Evaluation • Echocardiogram (in patients with carcinoid tumors only) • Image guided tumor biopsy for genotyping (patients with known familial cancer syndrome (MEN1, VHL and NF1) and with available archival tissue are excluded) • Cardiac Evaluation (in patients that present with cardiac or pulmonary risk factors) • 30 mL of peripheral blood for research • 2-13 mL saliva for research studies
Within 2 weeks prior to treatment initiation	
 • Chromogranin A • VIP, urinary 5-HIAA, gastrin, somatostatin, fasting insulin, C-peptide (proinsulin) and or glucagon only in patients known to have functioning NETs or with a prior history of elevation of secreting biomarkers.

		
 • CT C/A/P or MRI
Treatment cycles based on tumor genotyping (1 cycle=28 days)		
Cycle 1	Day 1 within 2 weeks prior to treatment	
 • Clinical Assessment³ • CBC, Chemistries², free T4, T3, TSH • Urinalysis • 12 lead ECG • Concomitant Medications • Adverse Events • Urine or serum HCG in women of childbearing potential (within 3 days before treatment)
	Day 15 within 1 week prior to treatment	
 • Clinical assessment³ • CBC and Chemistries² • Urinalysis • Concomitant Medications • Adverse Events
Cycle 2	Day 1 within 1 week prior to treatment or cross-over treatment	
 • Clinical assessment³ • CBC, Chemistries², free T4, T3, TSH • Urinalysis • 12 lead ECG • Concomitant Medications • Adverse Events • Urine or serum HCG in women of childbearing potential (within 3 days before study drug initiation)
	Day 15 within 1 week prior to treatment	
 • CBC, • Chemistries, • Urinalysis • Concomitant Medications • Adverse Events
Cycle N	Day 1 within 1 week prior to treatment or cross-over treatment	
 • Clinical assessment³ • CBC, Chemistries², free T4, T3, TSH • Chromogranin A (every 3 months) • Urinalysis • 12 lead ECG • Concomitant Medications • Adverse Events • Radiological evaluation of treatment response⁵ • Urine or serum HCG in women of childbearing

		potential (within 3 days before study drug initiation)
Safety Follow Up Visit (approximately 30 days after last dose of study drug)		

 • Clinical assessment³ • CBC, Chemistries², free T4, T3, TSH • Urine or serum HCG in women of childbearing potential • Urinalysis • Radiological evaluation of treatment response⁵ (not applicable for patients that have progressed on 2 drugs) • Concomitant Medications • Adverse Events 		
Long Term Follow up		
Telephone contact or e-mail every 3 months to determine anti-cancer therapy and survival status		

¹ Radiological Evaluations to be completed as part of the screening.

- Brain MRI or CT (if clinically indicated)
- 68-Gallium DOTATATE scan per PI discretion
- Contrast CT scan or MRI of the chest, abdomen and pelvis (CT C/A/P)
- Bone scan for patients in whom bone metastases are suspected
- FDG PET scan

² Chemistries: Sodium (Na), Potassium (K), Chloride (Cl), Total CO₂ (bicarbonate), Creatinine, Glucose, Urea nitrogen (BUN), Albumin, Calcium total, Alkaline Phosphatase, ALT/GPT, AST/GOT, Total Bilirubin, Total Protein

³ Clinical assessments: Complete history (screening only) and physical examination including height (screening only), weight, vital signs and ECOG

⁴ Filling out of the advanced directives will be offered, but obtaining of it is not required. For details see Section **10.3**

⁵ A CT or MRI of the chest/abdomen/pelvis to reassess treatment response will be done every 3 months after treatment initiation

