Hematologic	Continue at the same dose level.	Withhold dose until toxicity is Grade ≤ 2 or has returned to baseline, then resume treatment at the same dose level ² . If the toxicity recurs with Grade 3 severity, at the discretion of the investigator, reduce the dose by 1 level	Withhold dose until toxicity is Grade ≤ 2 or has returned to baseline, then reduce the dose by 1 level and resume treatment ²

¹If after the first 8 weeks there is no response according to RECIST and toxicity remains \leq non-hematological Grade 1 or \leq hematological Grade 2 dose escalation to 50 mg/day may be considered.

² Patients who develop grade 4 hyperuricemia or grade 3 hypophosphatemia without clinical symptoms may continue study treatment without interruption at the discretion of the investigator. Nausea, vomiting, or diarrhea must persist at grade 3 or 4 despite maximal medical therapy. Patients who develop Grade 3 or 4 lymphopenia may continue study treatment without interruption. Complicated neutropenia includes duration of Grade 4 longer than 7 days or concurrent fever or infection.

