3.3.2.3 Dosing modifications

For patients who do not tolerate the protocol-specified dosing schedule, dose adjustments are permitted in order to allow the patient to continue the study treatment. Details of study treatment schedule adjustments and dose levels are provided in **Table 7**

Table 7: Everolimus Dose Levels

Dose Level	Daily Dose	Dispensed As
0 – Starting dose level for patients without hepatic impairment*.	10 mg	1 x 10 mg tablets or 2 x 5 mg tablets or 4 x 2.5 mg tablets
-1	5 mg	1 x 5 mg tablets or

		2 x 2.5 mg tablets
-2	5 mg every other day‡	1 x 5 mg tablets or 2 x 2.5 mg tablets
*See Section 3.3.2.1 for definition and starting doses for hepatic impairment.		
‡ Patients requiring dose reduction below this level will be removed from the study therapy		

If treatment is interrupted due to toxicity, everolimus should not be resumed until recovery to grade ≤ 1 , then reintroduce everolimus at the initial dose or lower dose level depending on toxicity type and Grade.

If a patient has already decreased 2 dose levels, no further dose reduction is permitted. Patients requiring a third dose reduction will be required to discontinue study treatment. The following Table provides the procedure to be followed for dose modification and re-initiation of everolimus in the event of toxicities suspected to be related to the study drug.

Table 8 and **Table 9** list the dosing guidelines for everolimus-related non-hematologic and hematologic toxicities.

Management of severe or intolerable adverse drug reactions (ADRs) may require temporary dose interruption (with or without dose reduction) of everolimus therapy.

The following sections summarize recommendations for dose interruption, reduction, or discontinuation of everolimus in the management of ADRs. General management recommendations are also provided as applicable. Clinical judgment of the treating physician should guide the management plan of each patient based on individual benefit/risk assessment.

Table 8: Dosing guidelines for everolimus-related non-hematologic toxicities

Toxicity	Action
Non-Infectious Pneumonitis	Please refer to 4.1.2.9
Reactivation of HBV or HCV flare	Please refer to 4.1.2.10
AST or ALT elevation Grade 1 (> ULN - 3.0 x ULN) Grade 2 (> 3.0 - 5.0 x ULN)	Maintain current dose level

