AST or ALT elevation Grade 3 (> 5.0 - 20.0 ULN)*	Interrupt everolimus administration until resolution to \leq grade 1 (or \leq grade 2 if baseline values were within the range of grade 2). If resolution occurs within ≤ 7 days, everolimus should be re-started at the dose level prior to interruption. If resolution takes > 7 days, or if event reoccurs within 28 days, hold everolimus until recovery to \leq grade 1 or baseline grade / value and reintroduce everolimus at one dose level lower. .
AST or ALT elevation Grade 4 (> 20 x ULN)*	Interrupt everolimus administration until resolution to \leq grade 1 (or \leq grade 2 if baseline values were within the range of grade 2). If resolution occurs within ≤ 7 days, everolimus should be re-started at one dose level lower. If resolution takes > 7 days, discontinue everolimus.

Toxicity	Action
Intolerable grade 2 mucositis, or grade 3 AE, except hyperglycemia or hypertriglyceridemia or hypercholesterolemia (see Section 4.1.2.6)	Interrupt everolimus administration until resolution to \leq grade 1 or baseline grade / value. If resolution occurs within \leq 7 days, everolimus should be re-started at the dose level prior to interruption. If resolution takes $>$ 7 days, or if event reoccurs within 28 days, hold everolimus until recovery to \leq grade 1 or baseline grade / value and reintroduce everolimus at one dose level lower.
Any other grade 4	Hold everolimus until recovery to grade \leq 1 or baseline value Reintroduce everolimus at one dose level lower, if available.
Grade 3 or 4 clinical liver failure (asterixis or encephalopathy/coma)	Discontinue everolimus
Recurrence of intolerable grade 2 mucositis or grade 3 event after dose reduction	Reduce dose to the next lower dose level, if available. The lowest possible dose level of everolimus is 2.5 mg daily. Below this level, everolimus must be discontinued. If toxicity recurs at Grade 3, consider discontinuation
Recurrence of grade 4 after dose reduction	Discontinue everolimus
Any non-hematologic toxicity requiring everolimus interruption for $>$ 28 days	Discontinue everolimus
* Should HCV flare be confirmed, the guidelines for flare must take precedence (4.1.2.10)	

Table 9 Dosing guidelines for Everolimus-related hematologic toxicities

Toxicity	Action
Grade 2 thrombocytopenia (platelets <75, ≥ 50x10 ⁹ /L)	No action

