4.1.2 Management of specific everolimus toxicities

Overall, safety data available from completed, controlled and uncontrolled studies indicate that everolimus is generally well tolerated at weekly or daily dose schedules. The safety profile is characterized by manageable adverse events (AEs). These AEs are generally reversible and non-cumulative.

Adverse events most frequently observed with everolimus are stomatitis, rash, diarrhea, fatigue, infections, asthenia, nausea, peripheral edema, decreased appetite, headache, dysgeusia, epistaxis, mucosal inflammation, pneumonitis, weight decreased, vomiting, pruritus, cough, dyspnea, dry skin, nail disorder, and pyrexia. . Overall, the most frequently observed laboratory abnormalities include decreased hematology parameters including hemoglobin, lymphocytes, platelets, and neutrophils (or collectively as pancytopenia); increased clinical chemistry parameters including cholesterol, triglycerides, glucose, aspartate transaminases, creatinine, alanine transaminases, and bilirubin; and decreased clinical chemistry parameters including phosphate and potassium. The majority of these AEs have been of mild to moderate severity (NCI CTC grade 1-2).

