4.1.2.5 Renal Failure Events

Cases of renal failure (including acute renal failure), some with fatal outcome, occurred in patients treated with everolimus. Renal function of patients should be monitored particularly where patients have additional risk factors that may further impair renal function.

Elevations of serum creatinine, usually mild, and proteinuria have been reported in patients taking everolimus. Monitoring of renal function, including measurement of blood urea nitrogen (BUN), urinary protein, or serum creatinine, is recommended prior to the start of everolimus therapy and periodically thereafter.

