4.1.2.8 Management of hyperlipidemia and hyperglycemia

Adverse Drug Reaction	Severity	Everolimus Dose Adjustment and Management Recommendations
Metabolic events (e.g. hyperglycemia, dyslipidemia)	Grade 1	No dose adjustment required. Initiate appropriate medical therapy and monitor.
	Grade 2	No dose adjustment required. Manage with appropriate medical therapy and monitor.
	Grade 3	Temporary dose interruption. Re-initiate everolimus at one dose level lower. Manage with appropriate medical therapy and monitor.
	Grade 4	Discontinue everolimus and treat with appropriate medical therapy.

Treatment of hyperlipidemia should take into account the pre-treatment status and dietary habits of the patient. Grade 2 or higher hypercholesterolemia (>300 mg/dL or 7.75 mmol/L) or grade 2 hypertriglyceridemia or higher (>2.5x upper normal limit) should be treated with a 3-hydroxy-3-methyl-glutaryl (HMG)-CoA reductase inhibitor (e.g. atorvastatin, pravastatin, fluvastatin) or appropriate triglyceride-lowering medication, in addition to diet.

Note: Concomitant therapy with fibrates and an HMG-CoA reductase inhibitor is associated with an increased risk of a rare but serious skeletal muscle toxicity manifested by rhabdomyolysis, markedly elevated creatine phosphokinase (CPK) levels and myoglobinuria, acute renal failure and sometimes death. The risk versus benefit of using this therapy should be determined for individual patients based on their risk of cardiovascular complications of hyperlipidemia.

Dyslipidemia (including hypercholesterolemia and hypertriglyceridemia) has been reported in patients taking everolimus. Monitoring of blood cholesterol and triglycerides prior to the start of everolimus therapy and periodically thereafter as well as management with appropriate medical therapy is recommended.

Hyperglycemia has been reported in patients taking everolimus. Monitoring of fasting serum glucose is recommended prior to the start of everolimus and periodically thereafter. More frequent monitoring is recommended when everolimus is co-administered with other drugs that may induce hyperglycemia. Optimal glycemic control should be achieved before starting a patient on everolimus.

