11.2.4 Toxicity

(Please see package insert for a complete list of toxicities)

Toxicity information is based on pooled safety data in cancer patients receiving everolimus (N=2470) in clinical studies including randomized, double-blind, placebo- or active comparator-controlled phase-III trials and phase-II studies related to the approved indications in oncology.

The most common ADRs (incidence $\geq 1/10$ and suspected to be related to treatment by the investigator) from the pooled safety data were (in decreasing order): stomatitis, rash, fatigue, diarrhea, infections, nausea, decreased appetite, anemia, dysgeusia, pneumonitis, hyperglycemia, weight decreased, pruritus, asthenia, peripheral edema, hypercholesterolemia, epistaxis, and headache.

The most common grade 3/4 adverse drug reactions (incidence $\geq 1/100$ to $< 1/10$ and suspected to be related to treatment by the investigator) were stomatitis, anemia, hyperglycemia, fatigue, infections, pneumonitis, diarrhea, asthenia, thrombocytopenia, neutropenia, dyspnea, lymphopenia, proteinuria, hemorrhage, hypophosphatemia, rash, hypertension, aspartate aminotransferase (AST) increased, alanine aminotransferase (ALT) increased and pneumonia.

The most common adverse events were stomatitis (in 64% of the patients in the everolimus group vs. 17% in the placebo group), rash (49% vs. 10%), diarrhea (34% vs. 10%), fatigue (31% vs. 14%), and infections (23% vs. 6%). The most common grade 3 or 4 drug-related adverse events were anemia, hyperglycemia, stomatitis, thrombocytopenia, diarrhea, hypophosphatemia, and neutropenia[55].

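### Phosphate is on none of the three scheduled chemistry lists, although the protocol names hypophosphatemia among everolimus's most common grade 3-4 events, so asymptomatic cases would be found only by unscheduled testing.

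*Combined protocol and SAP*

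**What the plan says.** Chemistries are spelled out three times: at screening (Section 2.2), before cross-over (Section 3.1.1), and for treatment cycles and the safety follow-up visit (Section 3.4, footnote 2). The lists are identical. They give sodium, potassium, chloride, total CO2, creatinine, glucose and urea nitrogen, and end "Albumin, Calcium total, Alkaline Phosphatase, ALT/GPT, AST/GOT, Total Bilirubin, Total Protein".

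On everolimus toxicity, Section 4.1.2 includes among the most frequent laboratory abnormalities "decreased clinical chemistry parameters including phosphate and potassium". It adds that most of the adverse events described there have been mild to moderate (grade 1-2). Section 11.2.4 lists grade 3-4 events twice. The first list covers reactions with an incidence from 1% to under 10% and includes hypophosphatemia. The second reads: "The most common grade 3 or 4 drug-related adverse events were anemia, hyperglycemia, stomatitis, thrombocytopenia, diarrhea, hypophosphatemia, and neutropenia".

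Some everolimus monitoring is recommended outside the calendar. Section 4.1.2.5 says "Monitoring of renal function, including measurement of blood urea nitrogen (BUN), urinary protein, or serum creatinine, is recommended". Section 4.1.2.8 recommends "Monitoring of blood cholesterol and triglycerides prior to the start of everolimus therapy and periodically thereafter", and also fasting glucose. Section 4.1.2.10 sets out hepatitis B and C monitoring. Phosphate has no such statement.

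One dose rule names the condition. Footnote 2 to the sunitinib Table 5 (Section 3.3.1) says: "Patients who develop grade 4 hyperuricemia or grade 3 hypophosphatemia without clinical symptoms may continue study treatment without interruption", at the investigator's discretion. For everolimus, Table 8 (Section 3.3.2.3) has a general row headed "Intolerable grade 2 mucositis, or grade 3 AE, except hyperglycemia or hypertriglyceridemia or hypercholesterolemia" and a row for any other grade 4 event. Neither mentions phosphate.

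**The concern.** Low phosphate without symptoms can be known only from a laboratory value. A site that ran exactly the listed panel would never obtain one, for a toxicity that the protocol itself calls common at grade 3-4. Two things are at stake.

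- **Patient care.** A case that needs treatment, or that the investigator would judge clinically significant, may not be seen until symptoms appear.
- **Ascertainment.** Clinical laboratory evaluations are a declared safety endpoint (Section 1.1.2), and Section 8 tabulates the worst grade of each toxicity by arm. If phosphate is measured only on suspicion, the hypophosphatemia count depends partly on who ordered the test, and a low count could reflect little testing.

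**Working it through.** The protocol gives no figure to reproduce here. The main check is a comparison of the text, followed by simple arithmetic for scale.

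**1. Is phosphate measured anywhere on schedule?** It is on 0 of the 3 chemistry lists. Alkaline phosphatase is on all three, but it is an enzyme and does not measure serum phosphate. The other scheduled tests do not measure serum phosphate either: blood count, INR, lipid panel, HbA1c, thyroid tests, urinalysis, 24-hour urine for protein, albumin and creatinine, chromogranin A, hormone markers, and hepatitis, HIV and pregnancy tests. The Cycle 2 Day 15 entry says Chemistries without the footnote mark, but no other panel is defined.

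**2. Is the gap specific to phosphate?** Section 4.1.2 names 13 frequent laboratory abnormalities, which divide as follows.

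| Abnormality | Monitoring in the protocol |
|---|---|
| Hemoglobin, lymphocytes, platelets, neutrophils (4) | Blood count |
| Glucose, AST, ALT, creatinine, bilirubin, potassium (6) | Chemistries |
| Cholesterol, triglycerides (2) | Lipid panel at screening; periodic monitoring recommended in Section 4.1.2.8 |
| Phosphate (1) | None |

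So 4 + 6 + 2 = 12 of 13 are covered, and phosphate is the only one left out.

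**3. Which dose rules need the result?** Table 5 footnote 2 does so directly, because its condition is grade 3 hypophosphatemia without symptoms. The Table 8 rows would apply only if a low value counted as an adverse event. Section 6.1 records an abnormal laboratory value as one only if it leads to discontinuation, is associated with symptoms, requires treatment, is associated with death or another serious event, or is judged of significant clinical impact. Even then, Section 3.3.2.3 says "Clinical judgment of the treating physician should guide the management plan of each patient based on individual benefit/risk assessment".

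**4. How many grade 3-4 cases might occur?** Inputs: n = 44 evaluable patients per arm (Section 8), and p from 1% to under 10% (Section 11.2.4). The band is shared by every reaction in that list, and no phosphate-specific rate is given, so the values of p below are assumptions within it. Expected cases = n × p. Chance of truly no case = (1 − p)^44.

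| p | Expected among 44 | Chance of no case |
|---|---|---|
| 1% | 0.44 | 64% |
| 3% | 1.32 | 26% |
| 5% | 2.20 | 10% |
| 7% | 3.08 | 4% |
| 10% (excluded limit) | 4.40 | – |

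Cross-over adds everolimus exposure. If an assumed half of 44 sunitinib patients switch, n = 44 + 22 = 66, giving 0.66 to under 6.6 cases. If all switch, n = 88, giving 0.88 to under 8.8.

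These are all grade 3-4 cases, with or without symptoms, detected or not. The documents give no basis for the share that is asymptomatic or would be missed.

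**5. Could it affect the one formal toxicity comparison?** Section 8 allows a trend test for a toxicity with 5 or more grade 3-4 patients. Counting only 44 first-line everolimus patients, the binomial chance of 5 or more is about 0.01%, 1%, 7% and 19% at p = 1%, 3%, 5% and 7%.

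**The case against.** The strongest reply is that the consequence is small. The calendar is a minimum, and investigators may order phosphate at any time. Both drugs are marketed, and Section 11 refers readers to the package inserts. Lipids, too, are absent from the on-treatment calendar. Safety is secondary and descriptive, and the trend-test threshold is unlikely to be reached over most of the band. Symptomatic cases should come to light through the adverse event review at visits. These points stand, and they keep the concern at the level of an inexpensive improvement. They do not remove it: lipids at least have a written recommendation for periodic monitoring, whereas phosphate has none, and testing on suspicion is least likely to find cases without symptoms.

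Two further objections narrow the point.

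- **Dosing.** A reader might infer that both drugs' dose rules presuppose a phosphate result. The documents support this only for Table 5 footnote 2. Table 8 is general and depends on the Section 6.1 criteria and on clinical judgment. The sunitinib footnote also permits continued treatment, so a grade 3 result would often leave the sunitinib dose unchanged. It does not cover grade 4 or everolimus.
- **The safety table.** A reader might infer that full testing would make the hypophosphatemia count complete. It would not: Sections 6.1 and 6.1.2 would keep some asymptomatic, untreated cases out even if every patient were tested. However, two of the Section 6.1 criteria, need for treatment and judged clinical impact, cannot be assessed without a result.

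**Conclusion.** The gap is real and limited. If the listed panel is followed exactly, asymptomatic low phosphate is never detected, and with discretionary testing it is detected unevenly. Some treatable or clinically significant cases could be missed, and the hypophosphatemia count would be hard to interpret.

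The scale is 0.44 to just under 4.4 grade 3-4 cases among 44 first-line everolimus patients, more with cross-over. This rests on a band that is not specific to phosphate, and Section 4.1.2 describes most such events as grade 1-2. It is an upper frame for the problem and does not estimate missed cases; that share cannot be derived.

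A reader might also take a zero count as proof of under-detection. The arithmetic does not support that: at 1%, no case at all would occur 64% of the time even with full testing. Nor does the protocol plan to claim good tolerability from this count. PFS and the sample size are unaffected. Confidence is medium, because a site's routine panel may include phosphate although the protocol does not say so.

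**What to change.** Add phosphate to the Chemistries lists in Sections 2.2 and 3.1.1 and in footnote 2 of Section 3.4, run on blood already drawn. Leave the recording rules in Sections 6.1 and 6.1.2 unchanged, so that phosphate is handled like other laboratory toxicities.

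The cost is one routine analyte and the same edit in three places, with no new visit or procedure. Possible side effects are a small laboratory charge and a few more everolimus interruptions, subject to clinical judgment.

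If phosphate is not added, state in the safety results that hypophosphatemia was not systematically assessed. That requires no change to patient procedures.
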